1.2.3 Clinical Study

Phase II clinical study of IVIEW-1201(1.0% Povidone Iodine Ophthalmic Gel Forming Sterile Solution) is currently underway for the treatment of acute adenoviral conjunctivitis. This indication was approved by the U.S. FDA on December 30th, 2018 to enter Phase II clinical trials directly, and then trials were conducted in the United States, India and China (approved on November 1st, 2019) in an international multi-center format.

Among them, the results of Indian clinical trial data showed that IVIEW-1201 (1.0% Povidone Iodine Ophthalmic Gel Forming Sterile Solution) has good safety for human use.

1.3 IVIEW-1201 (1.0% Povidone Iodine Ophthalmic Gel Forming Sterile Solution) Phase II Clinical Trial for the Treatment of Acute Bacterial Conjunctivitis

Comprehensive data from public literature and in vitro bacteriological evaluation tests show that IVIEW-1201 (1.0% Povidone Iodine Ophthalmic Gel Forming Sterile Solution) is a clinical drug with great potential for the treatment of acute bacterial conjunctivitis. Therefore, we plan to conduct a multicenter, randomized, parallel-group Phase II clinical trial to evaluate the efficacy and safety of IVIEW-1201 (1.0% Povidone Iodine Ophthalmic Gel Forming Sterile Solution) in the treatment of acute bacterial conjunctivitis, using ofloxacin eye drops as a positive control, to explore the efficacy and safety of IVIEW-1201 (1.0% Povidone Iodine Ophthalmic Gel Forming Sterile Solution) in the treatment of acute bacterial conjunctivitis and provide a basis for Phase III clinical trials.

2 . Objectives and Endpoints

2.1 Objectives

The objectives of this study are to evaluate the efficacy and safety of IVIEW-1201 in the treatment of acute bacterial conjunctivitis.

2.2 Endpoints

2.2.1 Primary Endpoints

Clinical cure rate: The proportion of subjects with a score of 0 (on a 3-point scale) for bulbar conjunctival congestion and 0 (on a 3-point scale) for conjunctival secretion/exudation at Visit 4/End of Treatment (EOT) (Day 8±1 day) and Visit 5/End of Study (EOS) (Day 14±1 day).

2.2.2 Secondary Endpoints

Clearance rate: The clearance rate of each major pathogenic bacteria at Visit 2, 3, 4 and 5: Stratified analysis shall be conducted according to the type of pathogenic bacteria and the visit time point, and the clearance rate of each kind of bacteria by the investigational drug at different times shall be calculated. Bacterial clearance is defined as positive bacterial culture at baseline and negative bacterial culture at the last visit. Bacterial clearance rate = (number of subjects cleared + number of subjects assumed to be cleared) / total number of subjects enrolled × 100%.

2.2.3 Exploratory Endpoints

Mean clinical improvement rate at Visit 2, 3, 4 and 5:

Clinical improvement rate = (pre-treatment score - post-treatment score) / pre-treatment score × 100%. The score of symptoms and signs is the sum of the scores for pain, foreign body sensation, photophobia, tearing, conjunctival congestion, conjunctival secretion/exudation and conjunctival edema.

Total effective rate (%) at Visit 2, 3, 4 and 5:

Total effective rate (%) = (number of subjects cured+ number of subjects markedly effective) / total number of subjects available for evaluation of efficacy × 100%. Comprehensive efficacy evaluation: defined as cured, markedly effective, effective and ineffective; Calculate the total effective rate; See Appendix 2: Evaluation criteria of comprehensive efficacy for judgment criteria.

3. Trial Design

3.1 Overall Design

A multi-center, randomized, parallel, positive drug-controlled study design is used. In this study, the test drug IVIEW-1201(1.0% povidone-iodine ophthalmic gel sterile solution) is selected for the test group and the positive control drug Ofloxacin Eye Drops is selected for the control group. There are a total of 120 subjects: 60 in the test group and 60 in the control group.

The subject population in this study are those aged 15 and above (inclusive) with a confirmed diagnosis of acute bacterial conjunctivitis. Subjects should complete the random allocation and initial administration of the investigational drug on the day of diagnosis.

This study will be divided into 5 visit phases, namely Visit 1 (screening/baseline period, Day 1), Visit 2 (Day 3), Visit 3 (Day 6), Visit 4/End of Treatment(EOT) (Day 8 ±1 day) and Visit 5/End of Study(EOS) (Day 14±1 day).

3.2 Choice of Comparator Drug

Ofloxacin eye drops are quinolone eye drops that work by inhibiting bacterial DNA gyrase and DNA replication. Due to its unique mechanism of action, it has a broad antibacterial spectrum and strong antibacterial activity, and has a strong antibacterial effect on both Gram-negative and Gram-positive bacteria. It is effective against infections caused by sensitive species of *Staphylococcus aureus*, *Streptococcus pyogenes*, *Streptococcus pyogenes*, *Enterococcus*, *Pneumococcus*, *Escherichia coli*, *Citrobacter*, *Klebsiella pneumoniae*, *Enterobacter*, *Serratia*, *Proteus*, *Pseudomonas aeruginosa*, *Haemophilus influenzae*, *Acinetobacter*, *Campylobacter*, and *Chlamydia*. Ofloxacin has no cross-resistance with other antibacterial drugs. It is currently widely used in the clinic to treat external eye infections such as bacterial conjunctivitis, keratitis, corneal ulcers, dacryocystitis, and postoperative infections.

After comprehensive consideration, ofloxacin eye drops produced by Santen Pharmaceutical (China) Co., Ltd. are selected as the positive control drug. In order to maintain the consistency of the medication regimen of the experimental group and the control group, the instructions are referred to determine: 1 drop/eye/time for the affected eye. The drug is administered once at the research center on the first day, and then administered once at least 3 hours apart until bedtime, with a maximum of 4 times; 4 times on the second day, with at least 3 hours between each administration; 3 times a day from the third day to the seventh day, with at least 3 hours between each administration, and the medication schedule is 7 days.

3.3 Treatment of Newly Infected Eyes

If a subject suffers from monocular disease at Visit 1 and the other healthy eye becomes infected and develops bacterial conjunctivitis after Visit 1 during the study, the newly infected eye shall be treated with the investigational drug of the subject's group, following the prescribed administration regimen for the group, i.e. "the drug shall be administered once in the study site on Day 1, and then at least once every 3 hours until bedtime, up to a maximum of 4 doses; the drug shall be administered 4 doses on Day 2, with an interval of at least 3 hours; the drug shall be administered 3 doses a day from Day 3 to Day 7, with an interval of at least 3 hours, with duration of administration of 7 days", until Visit 5. At Visit 5, if the investigator determines that the newly infected eye still requires continued treatment based on the subject's signs and symptoms, the investigator will determine the specific treatment regimen after the subject is removed from the study, but the use of IVIEW-1201 (1.0% povidone-iodine ophthalmic gel sterile solution) should be discontinued. Newly infected eyes are not included in the group test, but normal secretions are taken for bacterial culture.

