11.Adverse events refer to all adverse medical events that occur to subjects after the first medication. However, in order to protect the rights and interests of the subjects, the recording of adverse events in this study starts from the signing of the informed consent form.

12. After completing Visit 4, IVIEW-1201 (1.0% povidone-iodine eye gel sterile solution) needs to be discontinued. If the investigator determines that treatment is still needed based on the subject's symptoms and signs, the specific treatment plan will be determined by the investigator, and the subject needs to continue in the group until Visit 5 (Day 14±1).

ABBREVIATIONS

AE	Adverse Event
TEAE	Treatment-Emergent Adverse Event
CTCAE	Common Terminology Criteria for Adverse Events
CRF	Case Report Form
D	Day
EC	Ethics Committee
EDC	Electronic Data Capture System
eCRF	Electronic Case Report Form
EOS	End of Study
EOT	End of Treatment
FAS	Full Analysis Set
FDA	Food and Drug Administration
GCP	Good Clinical Practice
MedDRA	Medical Dictionary for Regulatory Activities
NSAID	Nonsteroidal Anti-inflammatory Drugs
PVP-I	Povidone Iodine
PPS	Per Protocol Set
Q1	25% quantile
Q3	75% quantile
SAE	Serious Adverse Event
SS	Safety Set
VAS	Visual Analogue Scale
BCVA	Best-corrected visual acuity
MRSA	Methicillin-resistant Staphylococcus aureus
IWRS	Interactive Web Response System
ETDRS	Early Treatment Diabetic Retinopathy Study

1. Introduction

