6.3 Visit 4 (D8 ± 1 day) End of Treatment

Subjects will return to the study site for a visit on Day 8±1 during the treatment period and complete the following:

- 1) Vital signs (temperature, heart rate, blood pressure)
- 2) Subjective Symptoms Score
- 3) Objective Clinical Score

- 4) Best-corrected visual acuity
- 5) Corneal fluorescein staining
- 6) Slit-lamp examination
- 7) Intraocular pressure measurement
- 8) Collection of conjunctival sac secretion
- 9) Return of investigational drug, recovery and check of diary card, and evaluation of drug compliance.
- 10) Recording of adverse events
- 11) Recording of concomitant medications

If a subject forgets to return the investigational drugs, they can be returned at Visit 5. The treatment with the investigational drug shall be terminated at the end of this visit. If the investigator determines that continued treatment is still required (IVIEW-1201 needs to be discontinued) based on the subject's symptoms and signs, the specific treatment regimen will be determined by the investigator and recorded in the eCRF. The subject will need to remain in the study until Visit 5/EOS (Day 14±1 day).

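### A newly infected eye is to receive a 7-day course until Visit 5, but the general rules stop and collect the drug at Visit 4, with no exception stated

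*Combined protocol and SAP*

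**What the plan says.** Section 3.3, repeated in the synopsis entry on newly infected eyes, covers a subject with one affected eye at Visit 1 whose other eye becomes infected later in the study. It requires that "the newly infected eye shall be treated with the investigational drug" assigned to the subject's group, on that group's regimen. The regimen is restated in full and closes "with an interval of at least 3 hours, with duration of administration of 7 days". The sentence then runs on "until Visit 5. At Visit 5, if the investigator determines that the newly infected eye still requires continued treatment", so 3.3 places both the decision on further treatment and the discontinuation of IVIEW-1201 at Visit 5. It sets no latest onset day.

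The visits are fixed in section 3.1 as "Visit 4/End of Treatment(EOT) (Day 8 ±1 day) and Visit 5/End of Study(EOS) (Day 14±1 day"). Section 6.3, on Visit 4, states: "The treatment with the investigational drug shall be terminated at the end of this visit". Its procedure list includes "Return of investigational drug, recovery and check of diary card, and evaluation of drug compliance". A return at Visit 5 is mentioned only for subjects who forgot at Visit 4. Flow chart footnote 12 adds: "After completing Visit 4, IVIEW-1201 (1.0% povidone-iodine eye gel sterile solution) needs to be discontinued". Footnote 9 describes the dispensed drug as used over Days 1 to 7.

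The flow chart allocates drug only at Visit 1, marks administration at Visits 1 to 3, and ends the compliance and diary checks at Visit 4. It marks drug return at Visits 4 and 5.

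**The concern.** A site that sees a second eye infected on, say, Day 6 has two instructions. Section 3.3 gives it a 7-day course, which passes Visit 4. Section 6.3 tells it to stop the drug and take it back at Visit 4. Both are current text, and nothing ranks one above the other.

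If sites resolve this differently, exposure to study drug between Visit 4 and Visit 5 depends on the site. Newly infected eyes are left out of the efficacy group, but the subject stays in the Safety Set (10.3.1), and adverse events are collected up to the last visit (9.1). Visit 5 is also one of the two time points in the primary endpoint (2.2.1). Any doses after Visit 4 would fall where the schedule has no re-supply, diary check or compliance assessment, so the data might not show who took drug in that period.

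**Working it through.** The plan gives no figure to reproduce here. The check is a calendar count.

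**Inputs.** Course length is 7 days, counted from the second eye's own Day 1 (3.3). Visit 4 is Day 8 ± 1, so Day 7, 8 or 9. Visit 5 is Day 14 ± 1, so Day 13, 14 or 15 (3.1).

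**Step 1: end of course.** A course started on study Day k covers Days k to k + 6.

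**Step 2: clash with the Visit 4 stop.** Dosing days remain after Visit 4 when k + 6 > V4, that is, when k > V4 − 6.

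| Visit 4 on | First start day that runs past it | Course |
|---|---|---|
| Day 7 | Day 2 | Days 2–8 |
| Day 8 | Day 3 | Days 3–9 |
| Day 9 | Day 4 | Days 4–10 |

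A course started at Visit 2 (Day 3) ends on Day 9. It passes a Visit 4 on Day 7 or 8 but fits one on Day 9. A course started at Visit 3 (Day 6) ends on Day 12 and passes Visit 4 anywhere in its window, by 12 − 9 = 3 to 12 − 7 = 5 days.

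**Step 3: fit before Visit 5.** The course is complete by Visit 5 when k + 6 ≤ V5, that is, when k ≤ V5 − 6.

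| Visit 5 on | Last start day that finishes by then |
|---|---|
| Day 13 | Day 7 |
| Day 14 | Day 8 |
| Day 15 | Day 9 |

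For later starts, the 7-day duration and the Visit 5 end point within 3.3 cannot both be met.

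**Step 4: the other reading of 3.3.** Steps 2 and 3 treat Visit 5 as an outer limit on a 7-day course. If 3.3 instead means dosing up to Visit 5 whatever the start day, it conflicts with the Visit 4 stop for every onset before Visit 4.

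**Step 5: which arm each stop covers.** The general sentence in 6.3 stops the investigational drug. Section 3.3 uses that term for whichever drug the subject's group receives. The parenthesis in 6.3, footnote 12 and the Visit 5 sentence in 3.3 name IVIEW-1201 only. Sections 5.1 and 5.2 label IVIEW-1201 as investigational and ofloxacin as control, so the term is not used consistently.

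**The case against.** The strongest reply is that a specific rule and a general rule can stand together: 3.3 is a special provision with its own regimen and end point, while 6.3 and footnote 12 govern the eye enrolled at baseline. Return boxes at both Visit 4 and Visit 5 might seem to fit this. The reading is possible, but no passage states it. Section 6.3 explains late return by forgetting, not by continued use, and its stop is not limited to one eye. The missing exception is the defect.

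Other parts of the reply stand and limit the point:

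- A reader might infer that ofloxacin is left without a stop at Visit 4, so that the plan itself treats the arms differently. The general sentence in 6.3 reasonably covers both arms. Only the IVIEW-specific clauses are silent on ofloxacin, which makes this a matter of loose wording.
- A reader might infer that late infections are not provided for. Section 3.3 partly provides for them: an eye still needing treatment at Visit 5 passes to the investigator's own regimen after the subject leaves the study.
- A reader might infer that Visit 5 is meant as an off-treatment assessment that these doses would spoil. No passage defines it so, and 6.3 already allows investigator-chosen treatment between Visits 4 and 5.
- Footnote 12 concerns discontinuation only; drug return comes from 6.3.
- Excluding the affected subjects at Visit 5 would condition on an event after randomisation that treatment may influence.

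**Conclusion.** The point holds as an internal inconsistency. For any second-eye course that runs past Visit 4, sections 3.3 and 6.3 cannot both be followed as written. That means starts from Day 2, 3 or 4 onward, depending on whether Visit 4 falls on Day 7, 8 or 9. The very earliest onsets can satisfy both rules if Visit 5 is read as a cap on the 7 days. A course begun after Day 7, 8 or 9 also cannot be completed by a Visit 5 on Day 13, 14 or 15.

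The count assumes that the 7 days run from the second eye's first treated day, as the restated regimen in 3.3 implies. How many subjects would be affected is unknown, because the documents give no second-eye infection rate. The effect on Visit 5 results or on adverse-event comparisons therefore cannot be sized. What is established is that exposure between Visits 4 and 5 can depend on which passage a site follows. A bias between arms is not established.

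**What to change.** Reconcile the synopsis entry and section 3.3 with section 6.3 (including drug and diary return), footnotes 9 and 12, and the flow chart rows for administration, compliance, diary and return. One instruction should then apply to a newly infected eye, stated explicitly for both arms. Which rule that is, and what happens to a course unfinished at Visit 5, is for the sponsor and investigators to decide.

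For the analysis, add an eCRF flag for any study-drug use after Visit 4, and list exposure and adverse events for flagged subjects by arm. Keep these subjects in the Visit 5 analysis.

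The cost is protocol wording, one eCRF field and one listing. Sample size and the primary test are unchanged.

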3.4 Number of Subjects

This study preliminarily observed the efficacy and safety of IVIEW-1201 (1.0% povidone-iodine ophthalmic gel sterile solution) in the treatment of acute bacterial conjunctivitis, and no statistical analysis on the sample size is performed. Based on the safety evaluation requirements, 60 cases were set in the experimental group and 60 cases in the control group.

3.5 Blinding

In this study, there are significant differences between the investigational drug and the positive control drug in color, taste, properties and the patient's feeling when applying the medicine. The patient can easily distinguish them, which make it very easy to break the blind. Therefore, a single-blind or blind subject design cannot be used. The excipient components of ofloxacin placebo are unknown and too difficult to obtain for a double-blind double-simulation design. Since there are marketed drugs with clear efficacy for acute bacterial conjunctivitis, there are ethical issues in using a double-blind design with a placebo of 1.0% povidone-iodine eye gel sterile solution as a control.

The study is a blinded (assessor) study design. This means that the investigators are authorized to be blinded and non-blinded. Blinded and non-blinded team members shall be relatively independent in their work, limiting non-essential communication and avoiding disclosure of blind information.

Blindness shall be established when subjects are randomized. Blindness should be maintained until the blinded data review is completed, the database is locked and the primary statistical analysis is completed; The scope of the maintenance includes the above evaluators and blinded data analysts. The unblinding will be performed after the blinded data review is completed and the database is locked, and will be performed twice through the operation of the central randomization system. The first unblinding shall be performed after the database is locked, and the unblinding area is divided into groups X and Y and sent to the blinded data analysts for statistical analysis; The second unblinding shall be performed after the completion of the primary statistical analysis, and the specific test group or positive control drug group corresponding to groups X and Y shall be determined.

4. Selection of Subject

4.1 Inclusion Criteria

Inclusion Criteria:

Potential study subjects must meet **all** of the following inclusion criteria to be enrolled in this study.

1. Volunteered to participate in the study and signed the Informed Consent Form after receiving a verbal and written explanation of this clinical trial. In cases where the subject is unable to sign the Informed Consent Form, his/her guardian may sign in accordance with relevant regulations.
2. Aged above 15 (inclusive), male or female.
3. A diagnosis of acute bacterial conjunctivitis based on clinical observations: a) a score of ≥ 1 for bulbar conjunctival congestion and ≥ 1 for conjunctival secretion/exudation in at least one eye (same eye); and b) increased purulent, mucopurulent or mucopurulent secretions are observed in the conjunctival sac of the affected eye in all patients.
4. Willing to cooperate in the completion of all procedures and visits required for the trial.

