1.2 IVIEW-1201(1.0% Povidone Iodine Ophthalmic Gel Forming Sterile Solution)

1.2.1 Introduction

[figure not shown]
IVIEW-1201 is a brownish aqueous clear solution for ophthalmic administration, containing 1.0% (by weight) povidone-iodine for topical administration. After shaking, it becomes a brown, uniform, transparent solution. The active ingredient is povidone-iodine, whose chemical name is a complex of 1-vinyl-2-pyrrolidone homopolymer and iodine, and has in vitro antibacterial effects on a variety of bacteria, yeasts, fungi and human adenoviruses.

Povidone-iodine gradually releases iodine in the solvent and can release 1.4 to 2.4 ppm of free iodine in water. The powerful bactericidal mechanism of free iodine is to oxidize the active groups of pathogen protoplasmic proteins and combine with the amino groups of proteins to denature them, thereby effectively killing bacteria and other pathogens. It has the characteristics of low irritation, light yellowing, easy cleaning and no allergic reaction. It can quickly kill hundreds of bacteria including *Staphylococcus aureus*, *Escherichia coli*, *Pseudomonas aeruginosa*, *Neisseria gonorrhoeae*, *Candida albicans*, etc.

Povidone-iodine is a commercially available iodine tincture that is routinely used in ophthalmic and general surgical procedures. A single drop of PVP-I (5% to 10%) is used as an eye disinfectant before ophthalmic surgery and is approved by the FDA for this indication. Povidone-iodine has been used for the acute and chronic treatment of a variety of human indications. Povidone-iodine solutions have been shown to be effective before eye surgery (5% PVP-I)^[2,3] and before/after eye surgery (1.25% PVP-I, 2.5% PVP-I, 5% PVP-I)^[4,5]. It is also effective in treating neonatal ophthalmia (2.5% PVP-I)^[6,7] and acute ocular infection (1.25% PVP-I)^[8]. It has been clearly demonstrated in the literature that PVP-I is, in fact, tolerated and non-toxic at concentrations below 2% (w/w)^[9-11]. According to the ophthalmic literature, the active antimicrobial

drug povidone-iodine [10-14] has been shown to be well tolerated in low concentrations in animals and has low toxicity.

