4.2 Exclusion Criteria

Subjects are excluded from the study if any of the following exclusion criteria are met.

1. Patients with systemic or ocular diseases, or functional disorders with comorbidities, or structural abnormalities that, in the judgment of the investigator, could adversely affect the course or results of the trial (e.g. hyperthyroidism, hepatitis, acute and chronic renal insufficiency).
2. Those who have a history of allergy or serious adverse reactions to any component of IVIEW-1201 (1.0% povidone-iodine ophthalmic gel sterile solution) and Ofloxacin Eye Drops; have a history of allergy or serious adverse reactions to quinolones; or have a cumulative total of three

or more allergies to other drugs, food and environment; or who are prone to allergic symptoms such as rash and urticaria;

3. Symptoms or signs of bacterial conjunctivitis for more than 72 hours prior to screening.
4. Suspected fungal, viral or acanthamoeba infections based on clinical observations;
5. Those with severe keratitis or corneal opacity affecting the study results;
6. Active inflammation of the cornea, iris, or anterior chamber;
7. Corrected visual acuity of less than 0.2 in either eye;
8. History of eye surgery within 3 months prior to screening;
9. Those who have a history of acute or chronic dacryocystitis;
10. Those who need to wear corneal contact lenses during the trial;
11. Those who have used antibiotic eye drops or glucocorticoid eye drops within 14 days, and oral or intravenous antibiotics within 72 hours prior to screening;
12. Systemic use of steroid drugs within 14 days prior to screening. Local use of eye steroid drugs or nonsteroidal anti-inflammatory drugs (NSAIDs) within 7 days before enrollment (nasally or bronchially inhaled steroid drugs are not allowed during the study);
13. Those with co-infections requiring treatment with other anti-infective drugs in the study;
14. Those who are using other drugs that may interfere with the efficacy or safety evaluation of the drug;
15. Participation in other interventional clinical trials within 30 days prior to the study;
16. Pregnant or lactating women, women with positive pregnancy tests and those planning to become pregnant (including male subjects); subjects who do not take effective contraceptive measures within 1 month before enrollment, or subjects (including male subjects) who are unwilling to take effective contraceptive measures within the next 6 months.

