7.2.2 Evaluation of specific etiological efficacy

(1) Bacterial culture positivity rate = the number of positive bacterial culture as a percentage of the total number of cases in the study.

(2) Bacterial species clearance rate = the total number of bacterial species cleared as a percentage of the total number of pathogenic species isolated at the end of treatment.

(3) Negative conversion rate of bacterial culture = The percentage of patients whose bacterial culture turns negative after treatment among those with positive bacterial culture before treatment.

(4) Stratified evaluation of pathogens

① Analysis of 120 patients at the end of all studies

Pathogen/Number of patients	Cleared	Not cleared	Replaced	Re-infected
Staphylococcus aureus				
Streptococcus pneumoniae				
Haemophilus influenza				
Corynebacterium				
Streptococcus hemolyticus				

② Observation of different pathogens for different duration of administration

Duration of administration / Number of patients	Staphylococcus aureus	Streptococcus pneumoniae	Haemophilus influenza	Corynebacterium	Streptococcus hemolyticus
Baseline					
Visit 2					
Visit 3					
Visit 4					
Visit 5					

8. Compliance

Compliance will be determined by subject self-report as recorded in subject diaries. Missing diary data may be collected by subject questioning. There will also be drug dispensing and return logs to be completed by the investigative site.

% = actual number of medication times / theoretical number of medication times × 100%.

A calculated result less than 80% or greater than 120% was considered to be poor compliance

9. Assessment of Safety

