10.3 Statistical Analysis

10.3.1 Selection of statistical analysis data set

- 1) Full Analysis Set (FAS): All subjects randomized and for whom the data of at least one post-dose efficacy indicator is collected. Only the following randomized subjects are excluded: Subjects who violates key eligibility criteria, who are not treated with the investigational drug, and who have no observed data after randomization.
- 2) Per Protocol Set (PPS): A subset of the FAS, excluding subjects with significant protocol violations that may affect the primary efficacy evaluation based on the FAS.
- 3) Safety Set (SS): All subjects who have used the study drug at least once.

The efficacy analysis is mainly based on the FAS, but also on the PPS; the SS is used for safety analysis.

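### The primary cure comparison has no prespecified analysis in baseline culture-positive subjects, so the cure result is not tied to confirmed bacterial disease

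*Combined protocol and SAP*

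**What the plan says.** **Entry.** Inclusion criterion 3 (section 4.1) asks for "A diagnosis of acute bacterial conjunctivitis based on clinical observations": scores of at least 1 for bulbar congestion and for secretion in the same eye, plus increased purulent-type secretions. Exclusion criterion 4 (section 4.2) removes "Suspected fungal, viral or acanthamoeba infections based on clinical observations". Both are clinical judgements.

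**Timing.** Section 3.1 states: "Subjects should complete the random allocation and initial administration of the investigational drug on the day of diagnosis". Neither step waits for a culture result. The same section describes the population as "those aged 15 and above (inclusive) with a confirmed diagnosis of acute bacterial conjunctivitis".

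**Analysis sets.** Section 10.3.1 defines the FAS as "All subjects randomized and for whom the data of at least one post-dose efficacy indicator is collected", with exclusions for key eligibility violations, no treatment or no data. The PPS is a subset of the FAS without significant protocol violations. Then: "The efficacy analysis is mainly based on the FAS, but also on the PPS". Section 10.3.4 compares cure by chi-square or Fisher's exact test in these two sets.

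**Cultures.** Secretions from both eyes of every subject are cultured, starting at Visit 1 (study flow chart; section 6.5.3). Section 7.2.2 defines a positivity rate as "the number of positive bacterial culture as a percentage of the total number of cases in the study". It also defines a negative conversion rate among subjects positive before treatment, and tables by pathogen.

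**Drugs.** Section 1.2.1 says povidone-iodine "has in vitro antibacterial effects on a variety of bacteria, yeasts, fungi and human adenoviruses", and section 1.2.2.2 reports inactivation of adenovirus in vitro. Section 3.2 describes ofloxacin as an antibacterial.

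**The concern.** The trial asks about efficacy in acute bacterial conjunctivitis and is meant to support Phase III. Its primary outcome is clinical cure, yet cure is read only in a population selected by clinical signs. A positive culture is not an eligibility criterion, so the FAS exclusion for eligibility violations does not remove culture-negative subjects.

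This matters more here than it would with two antibacterials of the same kind, because the plan describes the two drugs as having different spectra. Subjects without bacterial disease can act in either direction. If both arms do equally well in them, they pull the arms together and hide a bacterial difference. If the test drug helps some of them through another mechanism, they add a difference unrelated to bacteria. Neither similar nor different cure rates in the FAS would tell the Phase III planner which of these happened.

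**Working it through.** **Is there a planned figure to reproduce?** Only 60 + 60 = 120, which is consistent. Section 3.4 says that no sample size calculation was made and that the number rests on safety. The plan gives no alpha, cure rate, positivity rate or margin. Everything below except n = 60 per arm is therefore an assumption for illustration.

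**Does either efficacy set depend on culture?** The section 10.3.1 conditions are randomization, treatment, a post-dose value, eligibility and protocol adherence. The section 4.1 and 4.2 criteria contain no culture condition. So neither the FAS nor the PPS depends on culture, and section 10.3.4 names no other set for cure.

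**What does the FAS difference estimate?** Let f be the culture-positive fraction, d+ the cure difference in positives and d− the difference in negatives. With f equal in both arms,

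FAS difference = f × d+ + (1 − f) × d−.

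Take f = 0.5:
- d+ = 20, d− = 0: 0.5 × 20 + 0.5 × 0 = 10 points.
- d+ = 0, d− = 20: 0.5 × 0 + 0.5 × 20 = 10 points.

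The same FAS result fits a purely bacterial effect and a purely non-bacterial one. At f = 0.7 with d− = 0, the FAS difference is 0.7 × 20 = 14 points.

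**Precision of a culture-positive set.** The 95% half-width is 1.96 × √(2 × 0.75 × 0.25 / n), at an assumed 75% cure in both arms.

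| f | n per arm | Half-width (points) |
|---|---|---|
| 1.0 | 60 | 15.5 |
| 0.8 | 48 | 17.3 |
| 0.6 | 36 | 20.0 |
| 0.5 | 30 | 21.9 |
| 0.4 | 24 | 24.5 |
| 0.3 | 18 | 28.3 |

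**Power, as an illustration only.** Exact binomial power of the uncorrected chi-square test, two-sided 0.05. Assumed cure is 80% v 60% in positives, and f = 0.5. Test-arm cure in negatives is held at 80%, so the FAS compares 80% with the average of 60% and the control rate in negatives.

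| Cure in negatives | FAS rates, 60 per arm | FAS power | Culture-positive power, 30 per arm |
|---|---|---|---|
| 80% v 80% | 80% v 70% | 25% | 39% |
| 80% v 75% | 80% v 67.5% | 35% | 39% |
| 80% v 70% | 80% v 65% | 46% | 39% |

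At f = 0.7 with equal cure in negatives, the powers are 42% (80% v 66%, 60 per arm) and 52% (80% v 60%, 42 per arm). The advantage of the smaller set thus depends on what happens in the negatives, and it reverses at a 10-point difference.

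**The case against.** **The trial does produce culture-based results.** A reader might infer that nothing in this trial can be tied to bacterial conjunctivitis. The documents do not support that. Section 7.2.2 defines a negative conversion rate among baseline-positive subjects and tabulates outcomes by pathogen and visit. These are bacteriological outcomes, however, and say nothing about cure. Nor does the listed secondary endpoint fill the gap: bacterial clearance (section 2.2.2) is also not cure, and its rate divides by all enrolled subjects.

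**Non-bacterial cases are partly screened out.** Exclusion 4 and the purulent-secretion requirement should reduce them. This stands, but both work by clinical judgement on the day of entry, so they limit the problem without removing it.

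**The wording of section 3.1.** It is tempting to read "those aged 15 and above (inclusive) with a confirmed diagnosis of acute bacterial conjunctivitis" as a contradiction of the entry criteria. It may simply mean clinically confirmed that day. Likewise, defining a positivity rate allows for culture-negative subjects but does not say how many the sponsor expects.

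**Power.** One might argue that the culture-positive set is the more powerful one. The working shows that this holds only in some scenarios, and the trial makes no power claim. A set of about 30 per arm could not establish similarity either.

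**It can be done later.** The swabs exist, so cure by culture status is recoverable. Section 10.3.4 also refers other indicators to a Statistical Analysis Plan, and a set defined in some further document cannot be ruled out. But the primary analysis and its sets are specified in the text at hand without one. Subjects know their treatment (section 3.5), and a set chosen after the results are seen is less credible than one fixed in advance.

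**Conclusion.** The point holds for the primary cure result. As written, the plan gives a cure comparison in clinically diagnosed subjects and no prespecified view of cure in those with proven bacterial infection. The case rests on interpretability, not on power.

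How far the FAS result departs from the effect in bacterial disease cannot be known in advance: it depends on the positivity rate and on the effect in culture-negative subjects, neither of which the documents give. The viral mechanism is plausible from the sponsor's own description of the drug, but it is not demonstrated for this population.

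This is an exploratory Phase II trial and no data would be lost, so the change is one that should be made rather than one on which the trial depends.

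**What to change.** In section 10.3.1, add a supportive baseline culture-positive FAS: FAS subjects whose Visit 1 swab from an affected eye grows a pathogen. Define pathogen by an organism list, starting from the five groups tabulated in section 7.2.2, and by any growth threshold to be used. Fix both before unblinding. Whether Corynebacterium, which is in that table, qualifies a subject on its own needs an explicit decision. The sample is a Visit 1 baseline swab, so membership does not depend on treatment.

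Keep the FAS as the main set. In section 10.3.4, report for the new set the cure rate by arm, the difference and its 95% CI at Visits 4 and 5, beside the FAS. Also show cure by baseline culture status, so that the culture-negative result is visible.

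The cost is the definition, including some work on the organism list, and one more table. No new procedure or subject is needed. The downside is the wider interval shown in the working, so the set should be labelled supportive and not used for a claim of similarity.
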